7.3.2.2 Pulmonary Function Tests

The secondary efficacy endpoint, number of subjects with absolute decline of 10% predicted in FVC (i.e. $\text{FVC percent predicted}_{\text{baseline}} - \text{FVC percent predicted}_{\text{progression}} \geq 10\%$) over 52 weeks will be analyzed using the binary endpoint analyses described in [Section 7.3.2](#). Subject with absolute decline of 10% predicted in FVC at any scheduled visits will be considered as subject with absolute decline of 10% predicted in FVC regardless whether the percent predicted FVC decline is less than 10% afterward and before the study early termination.

7.3.3 Analysis of Time-to-Event Endpoints

The time-to-event endpoints will be analyzed using survival analyses methods. The Kaplan-Meier curve and number of subjects at risk at each visit will be presented. The proportion of subjects who progressed in each treatment group will be summarized.

Time to event will be analyzed by a cox proportional hazards model with terms for treatment (BG00011 vs. placebo) and randomization stratification factor. A stratified log-rank test will be used to compare the 2 treatment groups using randomization stratus as the stratification factor. The progression will be summarized descriptively for each stratum.

Censoring rules will be applied for all time-to-event endpoints, unless otherwise specified. Subjects who do not experience an event by early termination, will be censored at the date of last assessment during the treatment period. The start date for calculation of day to censor or event will be the date of first dose. If a subject who was not on background therapy at randomization initiate treatment with background therapy during the study, the study will be censored at the time of new background therapy initiation. If a subject who was on background therapy at randomization stop background therapy during the study, the study will be censored at the time of the background therapy stopped.

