The study was monitored by an independent data safety monitoring board (DSMB) and included safety evaluations that would enable detection of respiratory events (e.g., IPF exacerbation; changes in lung function, including decreases from baseline in FVC by $\geq 12\%$, total lung capacity by $\geq 8\%$, and diffusing capacity of the lungs for carbon monoxide [DL_{CO}] by $\geq 15\%$). Four cohorts completed dosing through 1.0 mg/kg. Prior to the completion of dosing in the fifth and highest dosing cohort (3.0 mg/kg), the study was stopped after meeting the prespecified protocol stopping

CONFIDENTIAL

The information contained herein may not be used, disclosed, or published without the written consent of Biogen MA Inc.

criteria, when 2 subjects experienced clinically significant sustained decreases from baseline respiratory status. Following the decision to stop the 3.0 mg/kg cohort and additional discussions with the DSMB, Biogen conducted a detailed analysis of the available PK, PD, and safety data from all cohorts and concluded that the potential benefit/risk of BG00011 was acceptable for dosing patients with IPF, with appropriate safety monitoring, at doses not exceeding 1.0 mg/kg. A summary of the PK, PD, and safety data for Study 203PF201 is as follows.

Pharmacokinetic data show that after repeated weekly SC administration, BG00011 exposure increased approximately proportionally to doses ranging from 0.015 to 1.0 mg/kg, but increased greater than proportionally at doses >1.0 mg/kg. After the last dose, the mean terminal $t_{1/2}$ of BG00011 ranged from 168 to 211 hours across the dose range (approximately 174 hours following repeated administration at doses <3.0 mg/kg). Serum concentrations were relatively sustained throughout the 168-hour sampling period, with the time to reach maximum observed concentration (T_{max}) after the last dose occurring at 24 to 48 hours.

In this study, BG00011 decreased the level of phosphorylated SMAD2 (pSMAD2) in BAL cells starting at the 0.3 mg/kg dose and achieved $\geq 70\%$ reduction at the 1.0 mg/kg dose. In addition, a substantial decrease in gene expression of several prespecified genes linked to TGF- β signaling was also observed between the 0.3 and 1.0 mg/kg doses. These decreases in pSMAD and gene expression established proof of biology.

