7.2. Study Duration, Study Visits, and Follow-Up

Study duration for an individual subject is approximately 65 weeks, including a Screening Visit up to 5 weeks prior to the first dose of study treatment, a Placebo-Controlled Treatment Period of 52 weeks, and a Safety Follow-Up Visit 8 weeks after the end of the Treatment Period.

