3 STUDY DESIGN

This is a Phase 2b randomized, double-blind, placebo-controlled study designed to evaluate the efficacy, safety, PK, and tolerability of BG00011 in subjects with IPF. Approximately 290 subjects who meet inclusion/exclusion criteria will be stratified by background therapy status (subjects receiving background therapy and subjects not receiving background therapy) and randomized in a 1:1 ratio of BG00011 to placebo (**Error! Reference source not found. of the protocol**).

Subjects will receive weekly injections of BG00011 or placebo for 52 consecutive weeks (a total of 52 doses). Study duration for an individual subject is approximately 65 weeks, including a Screening Visit up to 5 weeks prior to the first dose of study treatment, a Placebo-Controlled Treatment Period of 52 weeks, and a Safety Follow-Up Visit 8 weeks after the end of the Treatment Period.

A schematic of the study design is provided in Figure 1. Additional details on the study design and the schedule of study assessment is provided in the full protocol. Due to the early termination of the study, no interim analysis will be performed. This change supersedes the interim analysis planned in the schematic of the study design in the protocol.

Figure 1: Schematic for Study 203PF203

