6.1.1.4 Early Termination or Unscheduled Visits for Acute Exacerbation of IPF

In general, when data are summarized by analysis visit, the Early Termination Visit or Unscheduled Visits for Acute Exacerbation of IPF will be assigned to an appropriate scheduled analysis visit by using a window scheme provided in Table 1.

Table 1: Visit Windows for Early Termination or Unscheduled Visits

Scheduled Visit Time	Target study day	Analysis visit window (days)	
		Efficacy & Safety Data	PK Data
Baseline (Day 0)	1	Most recent non-missing value on/before the date of first dose	
Day 5*	6	N/A	[6,7]
Week 4	29	[2,43]	[8,43]
Week 8	57	[44,71]	
Week 12	85	[72,99]	
Week 16	113	[100,127]	
Week 20	141	[128,162]	
Week 26	183	[163,203]	
Week 32	225	[204,246]	
Week 38	267	[247,288]	
Week 44	309	[289,337]	
Week 52	365	[338,393]	
Safety Follow-up (Week 60)	421	
 • If subject who discontinued treatment due to reasons other than study termination by sponsor: > min (393, study day of each subject's week 52/EOT visit in treatment period) ** • If subject who discontinued treatment due to study early termination by sponsor: > min (393, study day of each subject's last dose) 	

*The Day 5 Visit is for blood collection only (for PK analysis) and may be done in the clinic or at home (by appropriate personnel). Sample collection should occur on Day 5 (not sooner), with a +1 day window allowed (i.e., collection should occur on Day 5 but may occur on Day 6).

** For subjects who discontinued the treatment due to reasons other than study termination by sponsor will go on to complete all scheduled visits until either week 52 or the study was terminated by sponsor due to the urgent safety measure whichever occurs first. The Week 52/ EOT visit in treatment period is defined as the last visit scheduled for either week 52 or study termination due to the urgent safety measure.

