7.3.3.2 Other Time-to-Event endpoints

The time-to-event types secondary efficacy endpoints listed as follows will be applied only by the Kaplan-Meier curve method where number of subjects at risk at each visit and the proportion of subjects who progressed in each treatment group will be summarized and presented.

- Time to first acute exacerbation (using modified diagnostic criteria for acute IPF exacerbation derived from [Collar 2007]), measured in days.
- Time to death or lung transplantation measured in days.
- Time to all nonelective hospitalizations, measured in days.
- Time to all nonelective respiratory hospitalizations, measured in days.

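### Deaths and lung transplantations in safety follow-up after early termination drop out of time to death or lung transplantation, even when they fall within 52 weeks of first dose

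*SAP*

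**What the plan says.** SAP Section 7.3.3 states the scope of its rules: "Censoring rules will be applied for all time-to-event endpoints, unless otherwise specified". The rule for subjects without an event is: "Subjects who do not experience an event by early termination, will be censored at the date of last assessment during the treatment period". Section 7.3.3.2 then lists "Time to death or lung transplantation measured in days" among endpoints that "will be applied only by the Kaplan-Meier curve method", and gives it no censoring rule of its own. Section 7.3.3.1 places lung transplantation or death inside the composite time to progression. That endpoint follows the same rule and also gets a Cox model and a stratified log-rank test.

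The design keeps observing subjects after treatment. SAP Section 3 plans "a Safety Follow-Up Visit 8 weeks after the end of the Treatment Period". Protocol Section 15.3.2 records serious adverse events to the last study visit, and Section 15.3.3.1 requires causes of death to be reported as such. In SAP Table 1 (Section 6.1.1.4), the follow-up window has a branch that begins "If subject who discontinued treatment due to study early termination by sponsor"; for those subjects it opens after the last dose, or after Day 393 if that is earlier.

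The objective in SAP Section 2 names the transplant-free survival rate at Weeks 26 and 52. SAP Section 1 reports that the trial was stopped on a DSMB recommendation because of an imbalance in a safety composite.

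**The concern.** A death or transplantation can be observed, dated and inside the 52-week horizon, and still be treated as if the subject had been event-free at an earlier clinic assessment. The reason is only that it came after early termination. A 52-week horizon justifies ignoring the follow-up of subjects who completed Week 52. It does not justify ignoring the follow-up of subjects stopped early by the sponsor, whose 8 weeks may lie wholly within it.

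The protocol's secondary-endpoint section (16.2.2.3) has no treatment-period cut-off of this kind. After a stop for safety, readers will look at death and transplantation by randomized arm. Events are likely to be few, so each one lost matters. Part of the follow-up is also still under drug exposure, since the mean terminal half-life in the Phase 2a study "ranged from 168 to 211 hours across the dose range" (Protocol Section 4.4.3).

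**Working it through.** The plan states no event rate, power or precision for this endpoint (the sample size in SAP Section 4 rests on FVC slope). There is therefore no figure of the plan's to reproduce.

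**1. Length and position of follow-up.** The Schedule of Events puts Week 52 at Day 364 and Week 60 at Day 420: 420 − 364 = 56 days, or 8 weeks. A subject stopped at Week T and followed for 8 weeks finishes at Week T + 8. This lies inside 52 weeks whenever T ≤ 44.

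**2. Share of a stopped subject's events that falls in follow-up.** Assume a constant hazard and censoring at the last dose. Expected events are then roughly proportional to time, so the share is 8/(8 + T).
- T = 26: 8/34 = 0.235, about 24%.
- T = 38: 8/46 = 0.174, about 17%.

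With the exact exponential form and a 3.5-year median survival, the Week 26 share is 22%, so the approximation serves. These are shares for subjects stopped at those weeks, not trial-wide figures.

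**3. Drug exposure during follow-up.** Five half-lives is an assumed convention; the documents do not state one.
- 168 h: 5 × 168/24 = 35 days.
- 174 h (reported below 3.0 mg/kg): 5 × 174/24 = 36 days.
- 211 h (top of the range): 5 × 211/24 = 44 days.

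If follow-up starts at the last dose, this covers 35/56 = 63%, 36.25/56 = 65% and 44/56 = 79% of it. For a Week 52 completer, whose last dose is at Week 51, subtract 7 days: 50%, 52% and 66%.

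**4. Absolute scale, illustration only.** Protocol Section 4.1 gives a median survival of about 3.5 years from diagnosis. The hazard is ln 2/3.5 = 0.198 per year, and the 56-day risk is 1 − exp(−0.198 × 56/365.25) = 3.0%. Using its 5-year survival of 50% to 30% instead gives 2.1% to 3.6%. If 145 subjects were each followed for 56 days, that is about 3 to 5 deaths (145 × 0.021 = 3.0; 145 × 0.036 = 5.2). These are general IPF figures. Entry required FVC of at least 50% predicted and excluded likely transplantation within 12 months, so the trial rate may be lower.

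**5. Effect on the estimates.** Under the constant hazard of step 2, cutting the Week 26 subject's observation removes 8/34 of expected events and 8/34 of the time at risk. The ratio of events to time is unchanged. The crude proportion with an event falls and the standard error grows, but no downward bias in the Kaplan-Meier curve follows.

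**6. Where the cut-off lies.** Section 7.3.3 defines neither early termination nor the end of the treatment period. Protocol Section 7.2.2 ends the treatment period with the End of Treatment Visit, and Section 7.2.4 allows that visit up to 4 weeks after discontinuation. A subject who stops on Day 150 could have it as late as Day 178 (150 + 28). A death on Day 170 could fall before or after the cut-off, depending on the reading.

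**The case against.** The strongest reply is that a reader might infer three things the documents do not support.

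First, that these deaths vanish from the trial. They do not. SAP Section 8.2 follows treatment-emergent events to the last follow-up visit, counts deaths in the overall table (also by randomization stratum), and lists them. That stands. However, these are counts and listings by treatment received, without testing or time-to-event estimates, and Section 8 names no summary of transplantations.

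Second, that the curves understate risk in both arms. A sponsor stop applied to all ongoing subjects is administrative and not driven by individual prognosis. Under the constant hazard used for scale, the curve is not biased. Ending event-free time at the last assessment, while dating events when they occur, would if anything push the estimated risk up. The documents contain nothing to show that deteriorating subjects miss assessments first. This stands too.

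Third, that a death three weeks after the last dose is certainly excluded. Table 1 is a scheme for visit summaries, not a censoring definition, and step 6 shows that the answer turns on undefined terms. A completer who died in follow-up before the study was stopped may also still count as an event.

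It can also be said that this is a secondary efficacy endpoint shown descriptively, and that the redacted Section 7.4 may contain another survival analysis. Both are fair and limit the weight of the point. Neither supplies the missing rule in Section 7.3.3.2.

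**Conclusion.** The point holds as a limited one. On either reading of early termination, a death or transplantation that follows it during safety follow-up is not counted in time to death or lung transplantation or in that component of time to progression. For subjects stopped by the sponsor by Week 44, the whole of an 8-week follow-up is inside the endpoint's own horizon.

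The consequence is fewer events, wider uncertainty and lower crude event proportions. Bias in the Kaplan-Meier curves would need informative censoring, which is not shown. The shares of 24% and 17% rest on a constant hazard and censoring at the last dose. If the treatment period runs to a later End of Treatment Visit, less of the lost time is under drug exposure, but the weeks after that visit are still lost. The exposure argument covers roughly the first half to two thirds of follow-up, somewhat more at the top of the half-life range, and it depends on the five-half-life convention. The documents give no trial-specific death rate, so the number of events affected is unknown.

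The improvement is worth making because it is cheap and uses dates already collected.

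**What to change.** In SAP Section 7.3.3.2, for time to death or lung transplantation:
- Count all events through last study contact, including the Safety Follow-Up Visit, truncated at Day 365 for the 52-week estimate.
- Censor event-free subjects at the last date known alive and transplant-free.
- Keep the treatment-period version as supportive.

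For time to progression, run the same rule for the death and transplantation component as a supportive analysis.

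In Section 7.3.3, state what early termination and end of treatment period mean for censoring: the study's termination date or the subject's own visit, and last dose or End of Treatment Visit.

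The cost is a sentence on the endpoint, the two definitions, one extra curve and the supportive run on the composite; no new visits, subjects or data are needed. SAP Section 1.1 allows a revised version with changes documented, and this one should be fixed before the Part I data are unblinded. The downside is that some of the added events occur off treatment, which is why the treatment-period version should stay alongside.

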16.2.2.3. Analysis of the Secondary Endpoints

Time to progression will be presented using Kaplan-Meier curves, a stratified log-rank test will be used to compare the 2 treatment groups using randomization stratum as the stratification factor. The proportion of subjects who progressed in each arm will be summarized. Each component of progression will be summarized descriptively. If a subject who was not on background therapy at randomization initiates treatment with background therapy during the study, the subject will be censored at the time of new background therapy initiation.

Other time-to-event types of endpoints, e.g., time to first acute exacerbation, time to death or lung transplant, nonelective hospitalization (due to respiratory causes and due to all causes), and

CONFIDENTIAL

The information contained herein may not be used, disclosed, or published without the written consent of Biogen MA Inc.

survival rate (death from all causes and death due to respiratory causes) at 26 weeks and 52 weeks will be analyzed similarly.

The number of subjects experiencing an absolute decline of 10% predicted in FVC will be analyzed using a logistic regression model, adjusting for the randomization stratification factor, patient age, and baseline FVC.

Other pulmonary function endpoints and the 6MWT at 52 weeks will be analyzed similarly to the primary endpoint. For other visits, an analysis of covariance model adjusting the randomization stratification factor, age, and FVC at Baseline will be used to compare the treatment groups. The cumulative distribution of subjects by change in absolute and percent predicted FVC from Baseline to Week 52 will be presented in graph form.

Details of the analyses, including the handling of missing data, will be described in a SAP.

[REDACTED]

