2 STUDY OBJECTIVES AND ENDPOINTS

Primary Objective	Primary Endpoints
To evaluate the efficacy of BG00011 compared with placebo in subjects with IPF.	Yearly rate of change in forced vital capacity (FVC, expressed in mL over 52 weeks) in subjects randomized to BG00011 compared with placebo.
Secondary Objectives	Secondary Endpoints
To evaluate the efficacy of BG00011 compared with placebo in subjects with IPF as determined by change in percent predicted FVC.	Yearly rate of change in FVC, expressed in percent predicted, over 52 weeks.
To assess progression-free survival in subjects who receive BG00011 compared with placebo.	
Time to progression, as defined by a composite endpoint, including any of the following events:
 
 • Absolute decline of 10% predicted in FVC (FVC percent predicted_{baseline} – FVC percent predicted_{progression} ≥10%). • Nonelective hospitalization for respiratory events. • Lung transplantation or death.
To assess the occurrence of IPF exacerbation (using modified diagnostic criteria for acute IPF exacerbation derived from [Collard 2007]) in subjects who receive BG00011 compared with placebo.	
 • Time to first acute exacerbation, measured in days. • Proportion of subjects with at least 1 acute exacerbation during the 52 weeks on study. • Number of exacerbations during 52 weeks.
To assess the incidence of absolute decline in FVC ≥10% in subjects who receive BG00011 compared with placebo.	Number of subjects with absolute decline of 10% predicted in FVC (FVC percent predicted _{baseline} – FVC percent predicted _{progression} ≥10%) over 52 weeks.
To assess the time to death or lung transplantation in subjects who receive BG00011 compared with placebo, and the transplant-free survival rate at Week 26 and Week 52.	Time to death or lung transplantation, measured in days.

To assess the time to nonelective hospitalizations in subjects who receive BG00011 compared with placebo,
	
Time to all nonelective hospitalizations and to nonelective respiratory hospitalizations, measured in days.

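### Time to death or lung transplantation is censored when background antifibrotic therapy starts or stops, and nothing readable in SAP 7.3.3 counts later events

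*SAP*

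**What the plan says.** SAP 7.3.3 sets the scope: "Censoring rules will be applied for all time-to-event endpoints, unless otherwise specified". Two of its rules concern background therapy (pirfenidone or nintedanib). A subject off it at randomization is censored on starting it. For a subject on it at randomization who then stops, the rule reads "stop background therapy during the study, the study will be censored at the time of the background therapy stopped"; the study here evidently means the subject.

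SAP 7.3.3.2 lists "Time to death or lung transplantation measured in days" among endpoints that "will be applied only by the Kaplan-Meier curve method", with no exception to the censoring. The stated objective in SAP section 2 includes the "transplant-free survival rate at Week 26 and Week 52". Time to progression (7.3.3.1), which contains death and transplantation as components, uses the same method.

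The SAP is built on protocol version 1. Section 16.2.2.3 of that version has only the initiation rule, written for time to progression: "the subject will be censored at the time of new background therapy initiation". It then names "time to first acute exacerbation, time to death or lung transplant, nonelective hospitalization" and survival rates, which "at 26 weeks and 52 weeks will be analyzed similarly". It has no rule for stopping.

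**The concern.** Kaplan-Meier needs censoring that is unrelated to prognosis. Protocol version 1, section 7.1, allows background therapy to be started when the investigator judges it clinically indicated, so a link between starting and worsening is plausible. For stopping, a link is possible but not shown; protocol section 4.3 points mainly to side effects. Section 7.1 also lets subjects continue after stopping, and nothing there removes those who start. Later deaths and transplantations are therefore not missing data; the rule sets them aside.

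At stake is the transplant-free survival estimate at Weeks 26 and 52. If changes follow worsening, it is too favourable. The between-arm contrast is distorted mainly if the link, or the rate of change, differs by arm. The endpoint will be read closely: SAP section 1 says the trial was stopped for an imbalance in a prespecified safety composite (components and direction not given there), and protocol section 7.3 names deaths and lung transplantations among the DSMB stopping events.

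**Working it through.** **Step 1: the texts side by side.**

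| | Protocol version 1, 16.2.2.3 | SAP 7.3.3 |
|---|---|---|
| Start of background therapy | Censor (time to progression; other endpoints handled alike) | Censor, all time-to-event endpoints |
| Stop of background therapy | No rule | Censor, all time-to-event endpoints |
| Exception for death or transplantation | None | None |
| Analysis counting later events | None | None in the readable text |

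SAP section 1 lets the SAP supersede the protocol's statistics, but no reason is given for the new stop rule. Section 7.4 is redacted, so nothing is claimed about it. The documents state no event rate for this endpoint, so there is no plan figure to reproduce.

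**Step 2: a guide to how many subjects stop.** Protocol version 1 aims for about 50% on background therapy (7.1). It reports discontinuation for adverse events of 14.6% (pirfenidone) and 21% (nintedanib) in other trials (4.3).

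- 0.50 × 14.6% = 7.3% of all subjects; 290 × 7.3% ≈ 21
- 0.50 × 21% = 10.5%; 290 × 10.5% ≈ 30

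The 8-week stable-dose requirement and the early termination make these an upper guide for stopping. No rate is given for starting.

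**Step 3: an illustrative model; every input below is assumed.** Subjects are stable, deteriorated, or have had the event.

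- Stable to deteriorated: rate w·h. Stable directly to event: (1 − w)·h. Deteriorated to event: 1/60 per day. The weight w is 80% or 50%; h is solved so that the 364-day risk is 5% or 10%.
- Background change: rate c = −ln(1 − p)/364 while stable and m·c once deteriorated, where p is the yearly probability of change before deterioration and m is 1, 5 or 10.
- The change itself does not alter the event rate.
- With P_S and P_D the probabilities of being event-free and unchanged in each state, the censored Kaplan-Meier risk tends to 1 − exp(−∫[(1 − w)·h·P_S + P_D/60]/[P_S + P_D] dt).

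Results for w = 80%. True risk is 10% at Week 52 and 4.44% at Week 26. The true between-arm difference is 10% − 5% = 5.0 points.

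| p | m | Events discarded | Week 52 reads | Week 26 reads | Difference, same link in both arms | Link in higher-risk arm only | Link in lower-risk arm only |
|---|---|---|---|---|---|---|---|
| 7.3% | 5 | 6.9% | 9.72% | 4.34% | 4.86 | 4.72 | 5.15 |
| 7.3% | 10 | 10.2% | 9.39% | 4.23% | 4.70 | 4.39 | 5.31 |
| 10.5% | 5 | 9.9% | 9.59% | 4.30% | 4.80 | 4.59 | 5.21 |
| 10.5% | 10 | 14.3% | 9.14% | 4.14% | 4.58 | 4.14 | 5.44 |

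A simulation of 2,000,000 subjects for the last row gave 9.16% and 14.4% discarded.

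- **No link (m = 1):** Kaplan-Meier is unbiased, and 4% to 6% of events are discarded.
- **w = 50%:** 6% to 11% discarded; Week 52 reads 9.49% to 9.83%; differences are 4.75–4.92 (same link), 4.49–4.83 (higher-risk arm only) and 5.09–5.26 (lower-risk arm only).
- **Higher change rates (p = 14.6% to 21%, w = 80%), link in one arm only:** 4.18–4.43 or 5.29–5.42 at m = 5; 3.37–3.83 or 5.60–5.83 at m = 10.

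**Step 4: in events.** 290 × 5% = 14.5 and 290 × 10% = 29 events over a full year. Without a link about 0.6 to 1.7 are lost. With one, the loss runs from 14.5 × 5.6% ≈ 0.8 to 29 × 14.3% ≈ 4. Early termination makes these fewer.

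**The case against.** **Other outputs.** The SAP also asks for the proportion of subjects who progressed and does not say whether that count stops at censoring. Deaths are tabulated and listed under SAP 8.2. A transplantation could appear among concomitant non-drug treatments (SAP 6.4), and a background start is a protocol deviation (SAP 6.6). This is true, but the proportion sits under the same censoring rule with nothing to say later events are included. The rest are counts or listings, not time-to-event estimates, and the safety outputs do not name transplantations.

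**Start censoring is prespecified.** It comes from the protocol, and the stop rule can be read as its mirror image, targeting outcome on unchanged background therapy. That is a coherent target, so the remedy is an addition and the censored analysis can stay. However, protocol 16.2.2.2 pairs its exclusion of FVC data after a background start with a sensitivity analysis that restores them. SAP 7.2.3 likewise keeps FVC data after its own named intercurrent events. Death and transplantation get no such companion.

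**The modelled change rates come from stopping,** where the link to prognosis is weakest. For an exacerbation, protocol 11.5.1.1 points to added therapy other than the two antifibrotics. This stands, and it is why the figures are only an illustration.

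**The shift is small against sampling error.** With 145 per arm the standard error of the difference is √[(0.05 × 0.95 + 0.10 × 0.90)/145] = 3.1 points. The tabulated shifts reach 0.86 points, under a third of that; the most extreme case (5.0 − 3.37 = 1.63) is about half. Inference is nominal (SAP 6.7), and the stopping decision has already been made. These points limit the severity. They do not justify leaving the censored curve as the only readable estimate.

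**Conclusion.** The concern holds. Observed deaths and transplantations after a background therapy change are excluded by a stated rule. Half of that rule is new and unexplained, and nothing readable in SAP 7.3.3 restores these events.

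The likely effect is modest. In the main scenarios a true 10% risk reads 9.1% to 9.8%, and a 5.0-point difference reads between 4.1 and 5.4. There is no bias if changes are unrelated to prognosis. These sizes rest on assumed event risks, change rates, link strengths and a 60-day mean from deterioration to event, over a full year of follow-up that early termination cut short. For time to progression the effect is probably smaller, because FVC decline and respiratory hospitalization are themselves events and will often be counted before a change. The point should be fixed because the endpoint matters here and the remedy is cheap; it does not threaten the trial's main conclusions.

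**What to change.** 1. In SAP 7.3.3.2, add an analysis of time to death or lung transplantation that does not censor at background therapy changes and otherwise keeps the SAP's censoring rules. Show it beside the censored version.
2. In SAP 7.3.3.1, add the same for time to progression.
3. Give the reason for the stop rule, or remove it.
4. Report by arm the number of background starts and stops, and the number of events after a change.

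Items 1 and 2 matter most. The cost is SAP wording and a few extra outputs from data already collected, since subjects keep a diary of background dosing. The downside is that the uncensored estimates include the effect of the background changes themselves; keeping the censored version beside them lets the reader see both.
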